10.1. Potential Risks

Devices used in this clinical study are commercially available Medtronic is not aware of any significant problems with this product. In the clinical study, the products will be used in accordance with their labeling, therefore no risks other than the risks typically associated with routine device use are anticipated.

Risks will be minimized by careful assessment by the subject's doctor prior to, during, and after the monitoring phase.

In addition, a part from the capnographic monitoring, subjects are treated according to general clinical practice, so no extra tests or follow-ups are required for the study. Therefore, no additional risks are associated with participation in this clinical study.

Version 3.0, 29 Nov 2016

PRODIGY CIP

COVMOPO0560

Possible risks associated with capnographic monitoring are:

- Mild to moderate skin irritation or discomfort (redness, itching, rash, pressure) associated with the pulse oximetry sensor or related to the application or removal of the sensor. The skin will be assessed before and after the application of the pulse oximetry sensors. Subjects with known skin contact allergies to medical grade adhesives will not be recruited.
- Mild to moderate skin irritation or discomfort involved in wearing a filterline similar to a supplemental O₂ tube with an added oral scoop to collect a gas sample near the mouth for CO₂ analysis. The design mitigation to reduce skin allergic reactions is the use of latex free, ISO 10993 compliant components. Design of the oral/nasal interface and low pump suction pressure for sampling are means to reduce risk of discomfort.

10.2. Potential Benefits

Subjects' participation in this study may offer no additional benefit in respect to the same treatments provided outside of the study.

Possible benefits for participating in this study include the following (although others are possible):

• Study subjects may benefit from the structured, well-controlled clinical surveillance provided during the first days of opioid therapy.

The information gained from this study could result in the improved management of subjects undergoing in-hospital opioid therapy. Additionally, information collected from this study may assist in the design of a subsequent outcome study, the design of new product(s)/therap(y/ies) and/or instructions for use.

10.3. Risk-Benefit Rationale

Medtronic believes that the potential risks associated with the conduct of this study are minimal using non-significant risk, non-invasive study devices for the following reasons:

- All the devices used in the study are commercially available and used within their intended use.
- Standard of care will be followed by the sites for the administration of opioid therapy. Additional surveillance will be provided for close monitoring and recording of the subjects clinical status.

11. Adverse Event Assessments

In this study the following Adverse Events (AE) will be collected:

- All AEs with an underlying respiratory cause
- All adverse device effects (ADE)
- All Serious Adverse Events (SAE) (including sepsis events or related to opioid therapy)

RD episodes will not be considered Adverse Events if the subject is asymptomatic and no actions are taken.

11.1. Definitions/Classifications

Definitions according to ISO 14155:2011 will be used in this study.

Where the definition indicates "device", it refers to anv product used in the study. See product description section 7 for product information.

Version 3.0, 29 Nov 2016

PRODIGY CIP

COVMOPO0560

Term	Abbreviation	ISO Definition
Adverse Event	AE	Any untoward medical occurrence, unintended disease or injury, or untoward clinical signs (including abnormal laboratory findings) in subjects, users or other persons, whether or not related to the investigational medical device.
		NOTE 1: This definition includes events related to the investigational medical device or the comparator. NOTE 2 : This definition includes events related to the procedures involved. NOTE 3: For users or other persons, this definition is restricted to events related to investigational medical devices.
Adverse Device Effect	ADE	Adverse event related to the use of an investigational medical device.
		NOTE 1: This definition includes adverse events resulting from insufficient or inadequate instructions for use, deployment, implantation, installation, or operation, or any malfunction of the investigational medical device. NOTE 2: This definition includes any event resulting from use error or from intentional misuse of the investigational medical device.
Serious Adverse Device Effect	SADE	Adverse device effect that has resulted in any of the consequences characteristic of a Serious Adverse Event.
Serious Adverse	SAE	An adverse event that
Event		a) led to death,
		 b) led to serious deterioration in the health of the subject, that either resulted in
		1) a life-threatening illness or injury, or
		 a permanent impairment of a body structure or a body function, or
		3) in-patient or prolonged hospitalization, or
		 medical or surgical intervention to prevent life- threatening illness or injury or permanent impairment to a body structure or a body function,
		c) led to fetal distress, fetal death or a congenital abnormality or birth defect.
		NOTE: Planned hospitalization for a pre-existing condition, or a procedure required by the CIP, without serious deterioration in health, is not considered a serious adverse event.
Unanticipated Serious Adverse Device Effect	USADE	Serious adverse device effect which by its nature, incidence, severity or outcome has not been identified in the current version of the risk analysis report.

Table 3. Definition of Adverse Events and Device Deficiency

Version 3.0, 29 Nov 2016

Term	Abbreviation	ISO Definition
		NOTE: Anticipated serious adverse device effect (ASADE) is an effect which by its nature, incidence, severity or outcome has been identified in the risk analysis report.
Device Deficiency	DD	Inadequacy of a medical device with respect to its identity, quality, durability, reliability, safety or performance.
		inadequate labelling.

11.2. Reporting of Adverse Events

AE information will be collected throughout the study and reported to Medtronic on an AE eCRF, one for each adverse event. It is the responsibility of the investigator to identify the occurrence of adverse events to ensure that the information is accurately documented in the medical record and on the eCRFs.

DD information will also be collected throughout the study and reported to Medtronic on a Device Deficiency eCRF. DDs require immediate reporting if they did not lead to an adverse event but could have led to a serious adverse device effect (SADE):

- if either suitable action had not been taken,
- if intervention had not been made, or
- if circumstances had been less fortunate

AE documentation will include the following information at a minimum:

- Date of event
- Time of the event
- Diagnosis and description (including confirmation of respiratory nature)
- Actions taken / treatment (including vital signs, and date and time of rescue related actions when applicable)
- Assessment of seriousness
- Relatedness to the event (including opioid therapy or device)
- Outcome or resolution and date of the resolution

For AEs that require immediate reporting initial reporting may be done by phone, fax, e-mail, or preferably on the eCRF completing as much information as is available. The completed AE eCRF must be sent to Medtronic as soon as possible.

In case the investigator requires information from the sponsor in an emergency situation, the investigator can contact Technical Services or the Medtronic Study Manager. Contact information will be provided under separate cover.

The sponsor will ensure timely Adverse Event reporting to meet global regulatory requirements.

A list of anticipated adverse events that are expected in nature is included in Appendix A of this CIP.

Table 4. Reporting Requirements for Events

Serious Adverse Device Effects (SADE), including Unanticipated Serious Adverse Device Effect (USADE):

Investigator submit to:

Version 3.0, 29 Nov 2016

PRODIGY CIP

Medtronic	Immediately after the investigator first learns of the event or of new information in relation with an already reported event.	
Regulatory Authority	As per local reporting requirement.	
EC/IRB	Submit to EC/IRB per local reporting requirement.	
Sponsor submit to:		
Regulatory Authorities	Reporting timeframe as per local requirement.	
EC/IRB	Submit to EC/IRB per local reporting requirement.	
Serious Adverse Events (SAE)	
Investigator submit to:		
Medtronic	Immediately after the investigator first learns of the event or of new information in relation with an already reported event.	
Regulatory Authority	As per local reporting requirement.	
EC/IRB	Submit to EC/IRB per local reporting requirement.	
Sponsor submit to:		
Regulatory Authorities	Reporting timeframe as per local requirement.	
EC/IRB	Submit to EC/IRB per local reporting requirement.	
Adverse Device Effects (/	ADE)	
Investigator submit to:		
Medtronic	Immediately after the investigator first learns of the event.	
Regulatory Authority	As per local reporting requirement.	
EC/IRB	Submit to EC/IRB per local reporting requirement.	
Sponsor submit to:		
Regulatory Authorities	Reporting timeframe as per local requirement	
EC/IRB	Submit to EC/IRB per local reporting requirement.	
All other AEs		
Investigator submit to:		
Medtronic	Submit in a timely manner after the investigator first learns of the event.	
Regulatory Authority	As per local reporting requirement.	
EC/IRB	Submit to EC/IRB per local reporting requirement.	
Device Deficiency with SADE potential		
Investigator submit to:		
Medtronic	Immediately after the investigator first learns of the deficiency or of new information in relation with an already reported deficiency.	
Regulatory Authorities	As per local reporting requirement.	
EC/IRB	As per local reporting requirement.	
Sponsor submit to:		

Version 3.0, 29 Nov 2016

Regulatory Authorities	As per local reporting requirement.	
EC/IRB	As per local reporting requirement.	
All other Device Deficiencies		
Investigator submit to		
Medtronic	Submit in a timely manner after the investigator first learns of the deficiency.	
Regulatory Authorities	As per local reporting requirement.	
EC/IRB	As per local reporting requirement.	

12. Data Review Committees

This study will have the following Committees: Clinical Event Committee and Steering Committee.

No Data Monitoring Committee will be installed for this study as no interventions intended to prolong life or reduce risk of a major adverse health outcome are evaluated, for which favorable or unfavorable study results suggest study termination. Nor are there safety concerns suggesting the need for a Data Monitoring Committee.

12.1. Clinical Event Committee

The Clinical Event Committeee (CEC) is an independent committee of experts not participating in the clinical study that provides adjudication of study specific endpoints and/or events utilizing study-specific or consensus definitions available in the field. The committee will consist of a minimum of three (3) non-Medtronic experts experienced in evaluating respiratory compromise, respiratory depression, and interpreting continuous monitor data.

The CEC roles are to:

- Review AE's to classify the event as respiratory or non-respiratory.
- Review AE's to determine the relatedness (including device or opioid therapy).
- Review Respiratory Depression (RD) episodes and classify them as such based on the primary endpoint definition of RD.

Composition, roles and responsibilities of CEC will be described in a separate charter.

12.2. Steering Committee

The Steering Committee is composed of physicians with expertise in the area of Anesthesiology and capnographic monitoring, who will assume a leadership role in the overall study.

The Steering Committee's roles are to:

- Develop the protocol along with the sponsor, to ensure its scientific and statistical soundness;
- Review the conduct of the study;
- Help identify and resolve problems with recruitment or performance.

Version 3.0, 29 Nov 2016

PRODIGY CIP

Composition, roles and responsibilities of Steering Committee will be described in a separate charter.

13. Statistical Design and Methods

13.1. Sample Size

The size of the study cohort has been calculated to provide independent samples for derivation and validation cohort. At the study closure, subjects will be randomly assigned (2:1) into two groups to create a derivation cohort with 2/3 of the subjects and an internal validation cohort with the other 1/3 allowing to the following calculation.

According to a generally accepted rule of thumb, at least 10 events per variable are expected to be entered into the logistic regression model²⁰. The three following endpoints from RD definition have been taken into consideration to calculate the sample size (since we assumed that the variations in respect to enrollment values could be mostly included into these):

- A. RR \leq 8 bpm for \geq 3 minutes
- B. $SpO_2 \le 85\%$ for ≥ 3 minutes
- C. etCO₂ \geq 60 mmHg for \geq 3 minutes

From literature the incidence of the above events is at minimum:

 $A = 1.4\%^{21}$.

 $B = 10\%^8$ (extrapolation from Figure 3 of Sun et al.).

C = 1% (since we could not find literature data we arbitrarily suppose a low incidence).

The probability that at least one event among A or B or C occur is the probability (P) of the union (U) of A and B and C minus the probability of their intersection (\cap) as follow:

 $P(A \cup B \cup C) = P(A) + P(B) + P(C) - P(A \cap B) - P(A \cap C) - P(B \cap C) - P(A \cap B \cap C) = 12\%.$

13.1.1. Derivation Cohort Sample Size

The size of the derivation cohort has been calculated to provide at least 10 events per variable that we expect to enter into the logistic regression model. Recording at least 120 RD events would allow around 12 predictor variables to be entered into logistic regression. Assuming an incidence of 12% of subjects with RD episodes and 12-variables for prediction rule, a sample size of 1000 subjects is needed for the derivation cohort.

The selection of 12 high risk variables for the prediction rule has been based on literature review^{1,4,7,16,17,22}:

- Age > 65 y.
- Known or suspected sleep-disordered breathing (OSA, snoring, etc.).
- High risk surgery \leq 24 hours.
- PCA or epidural or intrathecal therapy.
- Obese (BMI >30).
- Multiple opioid or concurrent CNS/sedating medication (benzodiazepines, sleep aids, muscle relaxant, etc.).
- High opioid dosage (>30mg oral morphine per day or equivalent).
- Major organ failure.
- Diabetes.
- Chronic heart failure or other significant cardiac disease.
- Smoke (> 20 packs per year).

Version 3.0, 29 Nov 2016

PRODIGY CIP

- COPD or other significant pulmonary disease (including respiratory events before ward admittance).

13.1.2. Validation Cohort Sample Size

Since the derivation cohort will be 2/3 of the total sample size, the derivation cohort will be 1/3 (500 subjects) of the total sample size. Considering a 10% of withdrawals/dropouts/screening failure, the total sample size needed is 1650 subjects.

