Statistics	The size of the study cohort has been calculated to provide independent samples for derivation and validation cohort. At the study closure, subjects will be randomly assigned (2:1) into two groups to create a derivation cohort with 2/3 of the subjects and an internal validation cohort with the other 1/3 allowing the following calculation.		
	The size of the derivation cohort has been calculated to provide at least 10 events per variable that we expect to enter into the logistic regression model. Recording at least 120 RD events would allow around 12 predictor variables to be entered into logistic regression. Assuming an incidence of 12% of subjects with RD episodes and 12- variables for prediction rule, a sample size of 1000 subjects is needed for the derivation cohort.		
	Since the derivation cohort will be 2/3 of the total sample size, the internal validation cohort will be 1/3 (500 subjects) of the total sample size. Considering a 10% attrition of (ie withdrawals/dropouts/screening failure), the total sample size needed is 1650 subjects.		

4. Introduction

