5.2.2. Secondary Endpoint(s)

- 1. RD risk subjects versus no-risk subjects will be compared in terms of:
 - Incidence of AE's and actions taken.
 - Healthcare resource utilization (including hospital length of stay, 30 days readmission rate and primary diagnosis upon readmission).
 - Subject mortality at 30 days.
- 2. The predictive value (sensitivity, specificity, etc.) of etCO2, RR, SpO2, and IPI will be correlated with the occurrence of RD and ORADE.
- 3. Cost associated with events and actions taken will be estimated retrospectively using standard cost data from different countries.

6. Study Design

PRODIGY is a prospective, post-market interventional, multi-center, international cohort study.

A derivation cohort will be used to derive the risk assessment tool. An internal validation cohort will be used for evaluating the prognostic value of the score for the prediction of RD. Capnography and pulse oximetry monitoring device data will be collected as well as clinical data related to respiratory depression. Subjects will be monitored per standard of care. Enrollment at any single site will be limited to 20% (approximately 330 subjects) to ensure poolability of the data across sites and reduce potential bias. Additional methods incorporated to minimize potential bias include the following:

- Systematic identification of potential subjects via screening
- Both surgical and non-surgical candidates are eligible as event rates may vary
- Adjudication of RD events by an independent review committee
- Diverse geographical site representation to account for difference in practice

Version 3.0, 29 Nov 2016

PRODIGY CIP

- Standard procedures and data collection requirements with a common electronic database for all sites
- Provision of product for all study subjects

Foreseeable factors that may compromise the outcome of the study include lack of enrollment or the lack of respiratory depression events.

Approximately 1650 subjects will be enrolled in up to 16 centers from the United States (US), Europe and Asia. Geographic distribution of sites is anticipated as 8 sites (50%) in the US, 5 (30%) in Europe and 3 (20%) in Asia. Additional locations may be added during the course of the study.

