From literature the incidence of the above events is at minimum: A = 1.4%, B = 10% and C = 1%. The probability that at least one event among A or B or C occur is the probability (P) of the union of A and B and C minus the probability of their intersection giving the probability of 12%.

Derivation cohort sample size: the size of the derivation cohort has been calculated to provide at least 10 events per variable that we expect to enter into the logistic regression model. Recording at least 120 RD events would allow around 12 predictor variables (as found from literature review) to be entered into logistic regression. Assuming an incidence of 12% of patients with RD episodes and 12-variables for prediction rule, a sample size of 1000 patients is needed for the derivation cohort.

Validation cohort sample size: since the derivation cohort will be 2/3 of the total sample size, the derivation cohort will be 1/3 (500 patients) of the total sample size.

Considering a 10% of withdrawals/dropouts/screening failure, the total sample size needed is 1650 patients.

7 Statistical Methods

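### The total of 1650 covers about 9.1% attrition, not the stated 10%: a 1% arithmetic slip with no material effect

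*Protocol*

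**What the plan says.** The derivation cohort is sized by events per variable. Protocol 13.1.1 says: "The size of the derivation cohort has been calculated to provide at least 10 events per variable that we expect to enter" into the logistic model, and then: "Recording at least 120 RD events would allow around 12 predictor variables to be entered into logistic regression". It continues: "Assuming an incidence of 12% of subjects with RD episodes and 12-variables for prediction rule, a sample size of 1000 subjects is needed" for derivation.

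The split is two to one (Protocol 13.1). The statistics entry of the synopsis adds that "the internal validation cohort will be 1/3 (500 subjects) of the total sample size". Protocol 13.1.2 and SAP section 6 give the same 500 but label that one-third cohort derivation, evidently meaning validation. The label does not affect the arithmetic.

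The attrition step is one sentence. In Protocol 13.1.2 it reads: "Considering a 10% of withdrawals/dropouts/screening failure, the total sample size needed is 1650 subjects". SAP section 6 repeats it: "Considering a 10% of withdrawals/dropouts/screening failure, the total sample size needed is 1650 patients". The synopsis gives the same 10% and the same total. Protocol section 6 treats the recruitment target as approximate: "Approximately 1650 subjects will be enrolled in up to 16 centers from the United States (US), Europe and Asia".

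**The concern.** To keep a required number after a fractional loss, the required number is divided by the fraction retained. Multiplying by one plus the loss gives a smaller total, because the loss then applies to the enlarged number. Here 1650 matches the multiplication exactly, so the stated total does not deliver the implied 1500 at the loss rate stated in the same sentence.

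What is at stake is whether the printed figures agree with each other. Anyone who checks the sizing from its own inputs will reach a different total, and will find the derivation cohort slightly under the 1000 subjects and 10 events per variable on which it was planned.

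**Working it through.** **Inputs**
- Candidate predictors 12, events per variable 10, incidence 12% (Protocol 13.1.1; SAP section 6)
- Derivation to validation 2:1 (Protocol 13.1)
- Attrition 10%, total 1650 (synopsis; Protocol 13.1.2; SAP section 6)

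**Reproducing the plan's figure**
- Events needed: 12 x 10 = 120
- Derivation cohort: 120 / 0.12 = 1000
- Both cohorts: 1000 / (2/3) = 1500, that is 1000 + 500
- Total: 1500 x 1.10 = 1650, an exact match

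**What 1650 yields at a 10% loss**
- Remaining: 1650 x 0.90 = 1485, which is 15 short of 1500
- Derivation: 1485 x 2/3 = 990; validation: 1485 - 990 = 495
- Expected derivation events: 990 x 0.12 = 118.8, which is 1.2 short of 120
- Events per variable: 118.8 / 12 = 9.9

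**What a 10% loss would require**
- 1500 / 0.90 = 1666.7, rounded up to 1667; 1667 - 1650 = 17, and 17 / 1650 = 1.0%
- Attrition that 1650 does cover: 1 - 1500/1650 = 9.1%

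**How the gap compares with other uncertainty**
- Sampling variation: the standard deviation of the event count is sqrt(990 x 0.12 x 0.88) = 10.2, against a gap of 1.2.
- Rounding of the 12%: Protocol 13.1 builds it from 1.4%, 10% and 1%. Under independence (an assumption) these combine to 1 - 0.986 x 0.90 x 0.99 = 12.15%, and 990 x 0.12147 = 120.3 events. With no overlap they sum to 12.4%, and 990 x 0.124 = 122.8. At the other extreme, complete overlap would give 10%, and 990 x 0.10 = 99. The range from the assumed overlap alone is far wider than the slip.

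**The case against.** The best case for leaving the text alone is that a full 10% may never be lost from the primary analysis.

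- Protocol 8.2 and 9.5 count a subject as enrolled only after consent and confirmed eligibility, so screen failures may not be among the 1650 at all.
- Protocol 9.12 says that withdrawals other than screen failures are not replaced, which suggests, without saying so, that screen failures may be.
- Monitoring lasts at most 48 hours (Protocol 9.6), so dropout between monitoring and the 30-day contact need not remove a subject from the primary analysis.
- SAP 7.1.3 keeps in the modified full analysis set patients who stop monitoring early or never start it, and uses data up to the last collection.

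The plan also has a route if events are few. Protocol 13.3 and SAP 7.2 and 7.10.1 allow the whole population to be used for derivation, with bootstrap validation. At 1485 subjects and 12% that is 178.2 events, or 14.9 per variable. Finally, the target is only approximate, and a gap of 17 fits within that.

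All of this stands as an argument that the practical effect is negligible. None of it makes 1650 the right total for the 10% that the sample-size text itself assumes, and that text counts screening failure within the 10%.

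A reader might go further and infer that the plan promises 120 derivation events and fails to deliver them. The documents do not support that. The sentence in Protocol 13.1.1 about recording 120 events is a condition: if that many are recorded, around 12 predictors can be entered. Under independence the 1.2-event gap also disappears once the 12% is left unrounded. Nor do the odds of reaching 120 bear on the attrition step. At a true 12%, the binomial chance of at least 120 events is 47% with 990 subjects and 51% with 1000. Near-even odds follow from sizing on an expected count, and correcting the attrition would barely change them.

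**Conclusion.** The point holds as a small arithmetic correction. On the plan's own inputs, 1650 covers about 9.1% attrition. A 10% loss leaves 1485 subjects (990/495) and about 119 expected derivation events, 9.9 per variable. Holding 1500 would take 1667.

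These figures take the 12% incidence as printed, a full 10% loss from the analysed cohort, and a total of 1500 that is implied by 1000 + 500. If effective loss is 9.1% or less, the shortfall does not arise. It gives no ground for saying that the study is undersized or needs more subjects, and no analysis or conclusion depends on it.

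**What to change.** In the synopsis, Protocol 13.1.2 and SAP section 6, make one of two edits:

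1. Keep 1650 and say that it allows for about 9% attrition. The 1500, 1000/500 and 120-event figures then agree without further change.
2. Keep 1650 and 10%, and state the yield: about 1485 subjects (990 derivation, 495 validation) and about 119 expected derivation events, 9.9 per variable.

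The conditional sentence on recording 120 events can stay. The same edit could correct the label of the one-third cohort in Protocol 13.1.2 and SAP section 6. The cost is wording only, with no change to enrolment, the cohort split or the analysis. Under the second option one printed figure becomes slightly less favourable.
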